3.2 Rationale of study design

The design of this trial has been selected to adequately assess the primary objective and follows the similar design of trials for substance use disorders ([American Psychiatric Association \(APA\) Practice Guidelines, 2006](#)). Furthermore, randomized subject and investigator blinded control design are considered as “validated method in stimulant abuse trials” and parallel treatment group design was selected due to the long duration of treatment.

The entire study treatment duration of 98 days will be conducted in an outpatient treatment setting, which is a commonly used setting in treatment of substance use disorders ([UNODC-WHO, 2016](#)) and appropriate for the purpose of this study. The outpatient setting in this study includes frequent visit schedule (twice/week) in conjunction with urine sample collection; weekly monitoring of medication and study assessment adherence and safety adverse event monitoring. As an outpatient setting may increase the likelihood of patients dropping out of treatment, weekly interventions of Positive Reinforcement techniques are introduced with the focus on patient's adherence to the protocol's procedures and medication compliance.

For primary objective, daily cocaine use will be determined using TLFB self-report, which is a "gold standard" for measurement of substance use ([Robinson et al 2012](#)). For secondary objective, cocaine use will be determined twice/week by urine drug screen

Commercially Confidential Information Frequency of urine sample collection was scheduled in accordance with the halflife of cocaine metabolites BE in urine (3-4 days).

Commercially Confidential Information

3.3 Rationale for dose/regimen, route of administration and duration of treatment

The dose selected (200 mg bid with modified release formulation) for evaluation in this study has been chosen based on the safety, tolerability of dose, regimen and pharmacokinetic data from completed healthy volunteers and patient studies including modeling and simulation of PK and RO profiles. A total of 2159 study subjects have been enrolled in a total of 42 completed human studies with AFQ056. Dosage of 200 mg bid have been shown to be safe and tolerable.

During clinical development, majority of the studies were conducted using immediate release (CSF, MF) capsule formulations for oral administration. Nevertheless, there were some challenges experienced with the immediate release formulation as most of the AFQ056-mediated AEs (dizziness, insomnia, and headache) appear to be peak plasma concentration dependent. As a result, a modified release (MR) formulation of AFQ056 has been developed

with the goal of reducing peak plasma concentrations while maintaining optimal exposure (i.e. reducing C_{max}/AUC ratio).

The maximum anticipated therapeutic dose levels of AFQ056 are 150 mg bid. (CSF formulation – immediate release), 100 mg bid. (MF- IR formulation) or 200 mg bid. (MR formulation).

Commercially Confidential Information

In the proposed CUD study it is assumed that patients will have certain levels of cocaine when receiving AFQ056. Chronic cocaine administration has been reported to induce CYP3A4 in rodents ([Pellinen et al 1996](#)) and P-glycoprotein, an efflux transporter. AFQ056 is primarily eliminated via metabolism catalyzed by multiple CYP isoenzymes (incl. CYP1A1, 2C9, 2C19, 3A4) and possibly by UGT isoenzymes. Thus one cannot rule out that the AFQ056 levels may be altered (lowered) in subjects with long term cocaine use. Thus lowering of AFQ056 levels may affect efficacy rather than posing a safety risk.

Up-titration regimen: Data from three patients studies (CAFQ056A2203, CAFQ056A2206 and AFQ056A2225) indicated that the up-titration period will allow patients to adapt towards any side effects and thus have a better chance of tolerating the target dose of 200 mg bid..

3.4 Rationale for choice of comparator

As there are currently no approved medications for the treatment of Cocaine Use Disorder, placebo is the only relevant comparator to be used in this study. .

3.5 Rationale for choice of background therapy

Not applicable.

3.6 Purpose and timing of interim analyses/design adaptations

Due to the small sample size for this type of population, no IA planned for this trial.

Commercially Confidential Information

3.7 Risks and benefits

The risk to subjects in this trial will be minimized by adherence to the eligibility criteria, close clinical monitoring. Women of child bearing potential must be informed that taking the study treatment may involve unknown risks to the fetus if pregnancy were to occur during the study, and agree that in order to participate in the study they must adhere to the contraception requirements outlined in the [Section 4.2](#) (Exclusion Criteria). If there is any question that the subject will not reliably comply, they should not be entered or continue in the study.

Sexually active males must be informed of the requirement to wear a condom for the following reasons:

- Prevent pregnancy in a female partner

AND

- Prevent delivery of investigational drug via seminal fluid to their partner as study treatment may involve unknown risks to the fetus if pregnancy were to occur

Although, AFQ056 has been tested in more than 2000 subjects, and it has been shown to be safe and well tolerated it may be unknown risk associated to AFQ056. The most frequent side effects of the study medicine include: headache, dizziness, initial insomnia, feeling drunk and euphoric mood. In addition visual hallucinations have been reported after single intakes of high doses of the study drug (3 to 4 times of the highest dose used in this study) and in chronic smokers. The different studies performed in healthy volunteers and patients showed that AFQ056 is well tolerated also when given over a period of several weeks.

Commercially Confidential Information

3.7.1 Blood sample volumes

A maximum of up to 500 mL of blood is planned to be collected over a period of 14 weeks of treatment, from each subject as part of the study. Additional samples may be required for safety monitoring.

Timings of blood sample collection are outlined in the [Assessment schedule \(Section 8.1\)](#).

A summary blood log is provided in the Site Operations Manual. Instructions for all sample collection, processing, storage and shipment information is also available in the Bioanalytics Study Specifications (BSS) and Central Laboratory Manual.

Commercially Confidential Information

3.7.2 Risks associated with study procedures

In this study the tests done at each visit are standard medical tests. The most unpleasant is often having blood samples taken. The risks of taking blood may include fainting, pain and/or bruising at the site of needle or canula insertion. Rarely, a small blood clot or infection could occur that would require treatment. at the site of the needle puncture. The blood pressure cuff may also cause discomfort or bruising to the upper arm. There is also a chance for redness or irritation of the skin where the sticky electrode patches are placed during the heart tracing test (electrocardiogram).

4 Population

CUD patients

A total of approximately 60 patients, aged of 18-65 inclusive with a diagnosis of CUD who use cocaine through snorting (intranasally) will be enrolled in the study.

The investigator must ensure that all subjects being considered for the study meet the following eligibility criteria(s). No additional criteria should be applied by the investigator, in order that the study population will be representative of all eligible subjects.

Subject selection is to be established by checking through all eligibility criteria at screening and baseline. A relevant record (e.g. checklist) of the eligibility criteria must be stored with the source documentation at the study site.

Deviation from **any** entry criterion excludes a subject from enrollment into the study.

4.1 Inclusion criteria

CUD patients eligible for inclusion in this study must fulfill **all** of the following criteria:

1. Understand the study procedures and provide written informed consent before any assessment is performed.
2. Male and female subjects, 18 to 65 years of age (inclusive) and diagnosed with Cocaine Use Disorder according to DSM 5 (Diagnostic and Statistical Manual of Mental Disorders, 5th Ed.).
3. Must use cocaine through snorting (intranasally), as primary route of administration.

4. Recent cocaine use confirmed by positive urine screen for 1 or more benzoylecgonine (BE).
5. Must be seeking treatment for cocaine dependence and have a desire to reduce or cease cocaine use as per goals assessed at baseline.
6. Must be abstinent from cocaine use for at least 3 days preceding 1st dosing (Day 1) as assessed by self-report TLFB. The two urine drug screen samples at v2 and v3 must show a decrease in BE level or both must be negative.
7. Must be in good health as determined by medical history, physical examination, at screening.
8. At screening and baseline, vital signs (systolic and diastolic blood pressure and pulse rate) must be within the acceptable ranges by the investigator considering the cocaine's increasing effect on pulse rate in order for the subject to qualify. The investigator may be guided to use the below ranges:
 - systolic blood pressure, 90-150 mmHg
 - diastolic blood pressure, 50-90 mmHgThree readings are acceptable. At least the one of three readings must be within the acceptable ranges.
9. Patients must be able to:
 - communicate well verbally with the Investigator and to understand written instructions.
 - verbalize a willingness to complete all study procedures.
 - verbally acknowledge that she/he will be able to attend each scheduled visit, and that she/he does not have any already scheduled events or activities that may substantially interfere with study participation.

4.2 Exclusion criteria

CUD patients fulfilling any of the following criteria are not eligible for inclusion in this study:

1. History of hypersensitivity to any of the study treatments or excipients or to drugs of similar chemical classes.
2. Has current diagnosis moderate or severe Substance Use Disorder (according to the DSM 5) on alcohol, cannabis, opioids or other stimulants, except cocaine.
3. Meets current or lifetime DSM 5 criteria for schizophrenia or any psychotic disorder or organic mental disorder.

Notes: Subjects diagnosed with other psychiatric disorders may be included at the discretion of the PI provided that the concurrent treatment for the comorbid psychiatric condition will not interfere with completion of the study or place the patient at heightened risk through participation in the trial.

4. Have current treatment for Substance Use Disorder (e.g.: disulfiram, acamprosate, methylphenidate, modafinil, topiramate, immediate release dexamfetamine, or baclofen).
5. Requires treatment with any psychoactive medications, including any anti-seizure medications (with an exception of medications used for short-term treatment of insomnia)

Note:

- SSRI's are allowed if they have adequate stable dose for at least 1 month prior to study treatment dosing
6. Use of other investigational drugs at the time of screening, or within 5 half-lives of enrollment, or within 30 days, whichever is longer; or longer if required by local regulations.
 7. Pregnant or nursing (lactating) women, where pregnancy is defined as the state of a female after conception and until the termination of gestation, confirmed by a positive hCG laboratory test
 8. Women of child-bearing potential, defined as all women physiologically capable of becoming pregnant, unless they are using **effective methods*** of contraception during dosing and for 30 days after last dosing of study medication.

*Effective contraception methods include:

- Total abstinence (when this is in line with the preferred and usual lifestyle of the subject). Note: Periodic abstinence (e.g., calendar, ovulation, symptothermal, post-ovulation methods) and withdrawal are not acceptable methods of contraception
- Female sterilization (have had surgical bilateral oophorectomy with or without hysterectomy) or tubal ligation at least six weeks before taking study treatment. Note: In case of oophorectomy alone, only when the reproductive status of the woman has been confirmed by follow up hormone level assessment
- Male sterilization (at least 6 months prior to screening). For female subjects on the study, the vasectomized male partner must be the sole partner for that subject
- Barrier methods of contraception: Condom or Occlusive cap (diaphragm or cervical/vault caps) with spermicidal foam/gel/film/cream/ vaginal suppository; Placement of an intrauterine device (IUD) or
- intrauterine system (IUS)

Hormonal contraceptives that are injected or implanted or administered orally or transdermally **cannot** be considered as effective methods of contraception if taken with study medication.

Women are considered post-menopausal and not of child bearing potential if they have had 12 months of natural (spontaneous) amenorrhea with an appropriate clinical profile (e.g. age appropriate, history of vasomotor symptoms)

Note: In case the local requirement differs from the contraception methods listed above, local regulations would apply and it will be described in the ICF.

9. History of Porphyria.
10. History or presence of malignancy of any organ system, (other than localized basal cell carcinoma of the skin or in-situ cervical cancer), treated or untreated, within the past 5 years, regardless of whether there is evidence of local recurrence or metastases
11. Have a history of any illness, condition, and use of medications that in the opinion of the investigator or designee might confound the results of the study or pose additional risk in administering the investigational agents to the subject or preclude successful completion of the study
12. Any surgical or medical condition which might significantly alter the absorption, distribution, metabolism, or excretion of drugs, or which may jeopardize the subject in

case of participation in the study. The Investigator must make this determination in consideration of the subject's medical history and/or clinical or laboratory evidence of the following, at screening:

- Clinical laboratory values (including AST, ALT, total bilirubin or creatinine) considered as not clinically acceptable for CUD population, in the opinion of the Investigator, at screening:
 - ALT, serum bilirubin must not exceed 2 x ULN
 - GGT, AST and alkaline phosphatase must not exceed 5 x ULN.

In the case where a safety laboratory assessment at screening is outside of the range specified above, the assessment may be repeated once prior to randomization. If the repeat value remains outside of the specified ranges, the subject is excluded from the study.

13. Current or/and previous treatment with concomitant medications that are strong or moderate inducers/inhibitors of CYP3A4 (e.g., clarithromycin, ketoconazole, ritonavir, etc.).

Note: Concomitant medications that are strong or moderate inducers/inhibitors of CYP3A4 should have been stopped at least 5 half-lives prior to first dosing.

14. Concomitant use of agents known to prolong the QT interval unless these can be permanently discontinued for the duration of study.
15. History or current diagnosis of ECG abnormalities, at screening or baseline, indicating significant risk of safety for subjects participating in the study such as:
- Concomitant clinically significant cardiac arrhythmias, e.g. sustained ventricular tachycardia, and clinically significant second or third degree AV block without a pacemaker
 - History of familial long QT syndrome or known family history of Torsades de Pointes
 - QTcF > 450 msec (males) ; QTcF > 460 msec (females)

Note : sinus tachycardia, left axis deviation, and nonspecific ST or T wave changes are not exclusionary

16. Known history or presence of cardiovascular or cerebrovascular disease such as: angina pectoris, myocardial infarction, stroke, transient ischemic attack, peripheral vascular disease.
17. History of immunodeficiency diseases, including a positive HIV (ELISA and Western blot) test result.
18. Chronic infection with Hepatitis B (HBV) or Hepatitis C (HCV).
19. Score "yes" on item 4 or item 5 of the Suicidal Ideation section of the C-SSRS, if this ideation occurred in the past 6 months, or "yes" on any item of the Suicidal Behavior section, except for the "Non-Suicidal Self-Injurious Behavior" (item also included in the Suicidal Behavior section), if this behavior occurred in the past 2 years.
20. Patient cannot :
- anticipate any significant problems with transportation arrangements or available time to travel to the study site and have any plans to move within the next months to a location which would make continued participation in the study impractical
 - be involved in any unresolved legal problems that could jeopardize continuation or completion of the study

21. Patients with controlled hypertension i.e. patient diagnosed for hypertension and taking anti-hypertensive treatment must be excluded from this study.

No additional exclusions may be applied by the investigator, in order to ensure that the study population will be representative of all eligible patients.

5 Restrictions for Study Subjects

For the duration of the study, the subjects should be informed and reminded of the restrictions outlined in this section.

5.1 Contraception requirements

Women of child bearing potential must be informed that taking the study treatment may involve unknown risks to the fetus if pregnancy were to occur during the study, and agree that in order to participate in the study they must adhere to the contraception requirement outlined in the [Section 4.2](#) (Exclusion Criteria). If there is any question that the subject will not reliably comply, they should not be entered or continue in the study.

5.2 Prohibited treatment

Use of the following treatments/therapies are NOT allowed during the study:

- **Cognitive Behavioral Therapy (CBT)** or other similar interventional behavioral therapy(ies). Group therapies and support groups (such as AA) are allowed, provided the patients have been on such therapies for at least 3 months before screening, and therapies are continuing during the conduct of the study.
- **Glutamatergic drugs** due to potential mechanistic interactions with AFQ056
- **Moderate or strong inducers/inhibitors of CYP3A4** – potential for increased/decreased metabolism of AFQ056 (see [Section 17](#))
- **Lithium**– narrow therapeutic windows and not enough data regarding potential interactions between AFQ056 and these compounds
- **Unstable** treatment (unstable dose) with domperidone, antidepressants, and anxiolytics (see below *) – multiple potential interactions confounding the safety of AFQ056, especially when doses are adjusted
- Typical or atypical neuroleptic agents – risk of malignant neuroleptic syndrome when dopaminergic medication is adjusted
- Any pharmacotherapy with a potentially effective drug for cocaine dependence (i.e. disulfiram, acamprosate, methyl phenidate, modafinil, topiramate, immediate-release dexamfetamine, or baclofen) – potential for confounding the safety and/or efficacy of AFQ056

Notes:

SSRI are not allowed unless patients are on stable dose regimen and this dose is maintained over Screening and Baseline and being maintained stable during the treatment period.

Short-acting benzodiazepines used occasionally (e.g. against insomnia) are permitted

5.3 Dietary restrictions

- Cruciferous vegetable consumption (e.g. Brussel sprouts, broccoli, cabbage, cauliflower) should be limited to 1-2 times per week (due to the potential interaction with CYP 450 enzymes (Nakajima et al 2001)).
- No grapefruit or grapefruit juice is to be consumed for 14 days prior to dosing until 7 days following the last dose.
- In order to avoid wide variations in urine volumes, patients should be encouraged to have a fluid intake of approximately 240 mL every 4 hours during their waking hours, in addition to the fluid taken with meals and medication.

Dosing regimen:

Study medication will be provided in bottles. Patients should take one tablet in the morning with solid food (i.e. breakfast/morning meal) and one tablet in the evening with solid food (i.e. dinner/evening meal). The morning and evening doses should be taken at approximately 12-hour intervals. Study medication should be administered with a glass of water, and taken with a meal as described above. Patients should not chew the medication, but swallow it whole. Patients should avoid drinking grapefruit juice during the study.

Missed doses:

- If a patient misses a dose of study medication for any reason, the patient should not make up the missed dose with the next scheduled dose.
- If a patient misses a dose and realizes it within 3 hours, he/she should take the missed doses immediately; if a patient realizes it after 3 hours and more the doses is missed and a patient should take the next planned doses.
- The dosing regimen should be overseen by a caregiver, where appropriate, to ensure the dosing regimen is correctly followed.

5.4 Other restrictions

Not applicable.

6 Treatment

6.1 Study treatment

The investigational drug AFQ056 50mg, 100mg tablets and placebo will be prepared by Novartis and supplied to the Investigator as single blind patient specific medication pacs.

Details on the requirements for storage and management of study treatment, and instructions to be followed for subject numbering, prescribing/dispensing and taking study treatment are outlined in the SOM.

6.1.1 Investigational treatment and control drug(s)

Table 6-1 Overview of study medication

Study drug name	Formulation	mg per tablet	Packaging	Provided by
AFQ056 50mg	Tablet	50mg	Single blind patient specific kits	Novartis
AFQ056 100mg	Tablet	100mg	Single blind patient specific kits	Novartis
Placebo	Table	0mg	Single blind patient specific kits	Novartis

6.1.2 Additional study treatment

No additional treatment beyond investigational drug and control drug are included in this trial.

6.2 Treatment arms

Subjects will be assigned to one of the following 2 treatment arms in a ratio of 1:1.

- AFQ056 arm: up-titration bid regimen followed by fixed-dose bid regimen (50 mg bid from Day 1 to Day 7 followed by AFQ056 100 mg bid from Day 8 to Day 14, and then fixed-dose 200 mg bid for 84 days)
- Placebo arm: matching placebo

6.3 Treatment assignment and randomization

Randomized treatment will be assigned to individual subjects by way of a randomization number, which will be in the range of 5101-5300. Randomization numbers will be assigned to the different centers in multiples of the block size, depending on the recruitment of each site.

The Subject number assigned to a subject at screening remains the unique identifier for the subject throughout the study. For information on subject numbering, please see 'Subject numbering' section in the SOM.

Replacement randomization numbers will be in the range of 6101-6300. If a subject requires a replacement (for reasons other than safety or/and if the drop-out rate is higher than anticipated (20%higher), the replacement subject will be assigned a randomization number corresponding to the original subject (e.g. Subject 6103 would replace Subject 5103). Any additional subjects enrolled will use sequential subject numbering.

The table below details the general details of the numbering of the subjects once randomized to treatment:

Table 6-2 Randomization assignment numbering

Randomization numbers	Replacement randomization numbers
5101 – 5300	6101 – 6300

The randomization numbers will be generated using the following procedure to ensure that treatment assignment is unbiased and concealed from subjects and investigator staff. A randomization list will be produced by or under the responsibility of Novartis Drug Supply Management using a validated system that automates the random assignment of treatment arms to randomization numbers in the specified ratio.

The randomization scheme for subjects will be reviewed and approved by a member of the Randomization Office.

Follow the details outlined in the Site Operations Manual regarding the process and timing of treatment assignment and randomization of subjects

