11.4.2 Statistical model, hypothesis, and method of analysis

A Bayesian analysis will be conducted on the proportion of cocaine use days

Commercially Confidential Information

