11.5.1 Efficacy / Pharmacodynamics

11.5.1.1 Measure of cocaine in (BE) in urine

Two urine samples per week will provide a quantitative measure of cocaine's metabolite BE. The proportions of positive urine samples over the treatment period will be compared between groups using a t-test.

The quantitative BE profiles over time will be explored using visualization techniques and compared between groups using models appropriate to the distribution of the data.

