11.5.1.2 Measures of alcohol use

Alcohol consumption will be recorded by the patients using TLFB. The number of standard drinks will be recorded daily.

The proportion of days of alcohol consumption during the study treatment period will be compared between groups using an ANCOVA model with treatment as factor and past alcohol consumption as covariate.

The longitudinal profiles (daily number of drinks, weekly and monthly mean number of drinks) will be explored.

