11.7 Sample size calculation

A sample size of approximately 60 patients (30 patients on AFQ056 and 30 patients on placebo) was determined, assuming a SD of 32% ([Nuijten et al 2016](#)) for the proportion of cocaine use days. Patients who are withdrawn from the study for reasons other than safety may be replaced, if the drop-out rate is higher than anticipated (20 % higher).

Commercially Confidential Information

Commercially Confidential Information

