#### 6.2.2 Descriptive analyses

The log-transformed quantitative urine measurements of Benzoylecgonine will be summarized by treatment and visit / time and weekly. To obtain the weekly profiles, the BE measurements obtained by a subject during each week (aligned with the weekly profiles of TLFB) will be averaged. These data shall also be listed by subject, and time point.

Descriptive summary tables shall be provided to summarize the alcohol consumption by treatment and week, and by treatment and month. The alcohol daily consumption, weekly consumption and monthly consumption will be listed by subject and time point. If country is a significant effect in the model stated in section 6.2.3 then summary statistics will also be provided by country.

The amount spent on cocaine will be summarized by treatment and listed by subject and time point. The amount spent will be converted in Euros for the summary statistics, using the exchange rates recorded on 7th August 2019 from XE currency converter website (<https://www.xe.com/currencyconverter/convert>). The exchange rates are:

US Dollar to Euro – 0.891

Swiss Franc to Euro – 0.916

Argentine Peso to Euro – 0.019

The number and % of subjects abstinent the last x weeks will be described both on the PD analysis set and FAS.

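### Allocation is blocked within centres, but the protocol's urine t-test ignores centre and its alcohol ANCOVA leaves out the country effect that the SAP implies

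*Protocol*

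**What the plan says.** Protocol 6.3 describes the allocation: "Randomization numbers will be assigned to the different centers in multiples of the block size, depending on the recruitment of each site". Protocol 6.2 sets the ratio: "Subjects will be assigned to one of the following 2 treatment arms in a ratio of 1:1". The block size, the number of centres and any declared stratification are not given.

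Two between-arm efficacy comparisons can be read in the protocol:

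- Urine (11.5.1.1): "The proportions of positive urine samples over the treatment period will be compared between groups using a t-test".
- Alcohol (11.5.1.2): days with drinking are compared "using an ANCOVA model with treatment as factor and past alcohol consumption as covariate".

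Neither names centre or country. The longitudinal analyses of self-reported cocaine use (11.4.4) are called mixed models, but no model terms are listed.

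The SAP gives one clue. In its paragraph on alcohol, section 6.2.2 says: "If country is a significant effect in the model stated in section 6.2.3 then summary statistics will also be provided by country". So a country effect stands in a model of SAP 6.2.3, whose text is redacted. The primary model is redacted too; what remains in protocol 11.4.2 is "A Bayesian analysis will be conducted on the proportion of cocaine use days".

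**The concern.** Giving whole blocks to centres makes the two arms alike in their mix of centres. Differences between centres then largely cancel out of the treatment contrast. They do not cancel out of the pooled within-arm variance from which a t-test builds its standard error. The t-test therefore charges the treatment estimate for variation that the allocation has largely taken out of it. Intervals come out too wide and true effects are missed more often.

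In a trial of about 60 patients there is little precision to spare. The SAP converts cocaine spending from US dollars, Swiss francs and Argentine pesos into euros, so patients in quite different settings are expected, and levels of use may differ between them. For alcohol there is also an inconsistency: the protocol's model has no country effect, while the SAP's wording implies one.

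**Working it through.** **Inputs from the documents.** Protocol 11.7: "A sample size of approximately 60 patients (30 patients on AFQ056 and 30 patients on placebo) was determined, assuming a SD of 32" percentage points. Allocation is 1:1, in blocks within centres. The sample size of 60 cannot be reproduced, because the target effect and decision criterion are redacted.

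**Assumptions.** The documents do not give:

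- the share ρ of outcome variance lying between countries or centres (taken as 0 to 30%);
- the number and size of groups (4 countries of 15 patients, and separately 5, 6 or 10 equal centres);
- the block size (4 in the country setting);
- the test level for secondary comparisons (two-sided 5%).

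The SD of 32 is stated for cocaine-use days. Carrying it over to urine is a further assumption. It scales the standard errors but does not affect their ratios or the type I error.

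**Formulas.** Ignoring groups, SE = 32 × √(2/30) = 8.26 points. With exact balance within groups, the true SE is 32 × √(2(1−ρ)/30):

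- ρ = 0.05: 8.05
- ρ = 0.10: 7.84
- ρ = 0.20: 7.39
- ρ = 0.30: 6.91

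**Simulation: 4 countries of 15, blocks of 4, last block incomplete.** The power columns are for an illustrative 20-point difference.

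| ρ | Mean t-test SE | True SE | Type I, t-test | Type I, adjusted | Power, t-test | Power, adjusted |
|---|---|---|---|---|---|---|
| 0% | 8.22 | 8.15 | 4.8% | 4.8% | 67% | 67% |
| 5% | 8.2 | 8.1 | 4.5% | about 5% | 67.3% | 68.5% |
| 10% | 8.13 | 7.82 | 4.2% | 5.0% | 68% | 71% |
| 20% | 8.04 | 7.48 | 3.6% | 5.0% | 69% | 74% |
| 30% | 7.91 | 6.98 | 2.7% | 4.8% | 72% | 81% |

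The small gap between the two SEs in the first row is simulation noise around 8.26. Repeat runs put the type I error at 3.5-4% for ρ = 20% and near 3% for ρ = 30%.

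**Simulation: 5, 6 or 10 equal centres with exact balance, 20,000 trials each.** The t-test's type I error is 4.5-5.0% (ρ = 5%), 3.9-4.1% (10%), 3.1-3.2% (20%) and 2.3-2.9% (30%). With a fixed centre term it stays near 5%.

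**Equivalent sample size** = 60 × (mean t-test SE / true SE)²:

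- ρ = 10%: 60 × (8.13/7.82)² = 64.9, about 65
- ρ = 20%: 60 × (8.04/7.48)² = 69.3, about 70
- ρ = 30%: 60 × (7.91/6.98)² = 77.1, about 77

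**What changes.** In a separate run of the country setting, the empirical SD of the treatment estimate, unadjusted against adjusted, was 7.86 and 7.88 (ρ = 10%), 7.47 and 7.44 (20%), and 7.07 and 7.00 (30%). The estimate itself hardly moves. The gain lies in reporting the right standard error.

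**The case against.** Several points on the other side stand.

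- **The error is in the safe direction.** It costs power and interval width and adds no false positives. At ρ = 0 there is nothing to gain, and at 5% the power gain is about one percentage point.
- **The size rests on assumptions.** The documents give no between-centre variance, and the number of countries is inferred from exchange rates.
- **The balance is only approximate.** Small centres may leave blocks unfinished, withdrawn patients may be replaced, and the SAP's PD set drops patients for short dosing or poor compliance.
- **Country is coarser than centre.** Blocking is by centre, so a country term would recover only part of the between-centre variation.

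Four stronger readings are tempting, and the documents do not support them.

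1. A reader might infer that no efficacy analysis adjusts for centre or country. The primary model and SAP 6.2.3 are redacted, so their terms cannot be called missing, and SAP 6.2.2 points to a country effect for alcohol. Protocol 11.4.4 lists no model terms at all, so the absence of country there shows nothing.
2. A reader might take 60/(1−ρ), that is 67, 75 or 86 patients, as the gain. That compares with an unblocked design. Here the blocking has already reduced the variance of the estimate, whether or not the model is adjusted.
3. A reader might take the SAP's significance condition as a rule for dropping country from the model. It governs only whether extra descriptive tables by country are produced.
4. A reader might say that the design has fully removed centre variation. Given the loose balance noted above, that is too strong.

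**Conclusion.** The point holds for two readable comparisons. The protocol's urine t-test does not use the centre blocking, and the protocol's alcohol ANCOVA does not match the country effect that the SAP implies. If centres or countries differ, the urine comparison reports too large a standard error and is conservative.

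Over 0% to 30% of variance between four assumed countries, the t-test SE is overstated by nothing up to roughly 13% (7.91/6.98), and its type I error runs from about 5% down to about 3%. The loss is negligible at 5% between-country variance and moderate at 20% or more. This is a modest, nearly free improvement to secondary analyses. It is not a flaw shown in the primary analysis.

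**What to change.** 1. In protocol 11.5.1.1, replace the urine t-test with a linear model containing treatment and a prespecified centre effect. Make centre random, or use country as a fixed effect if centres are small.
2. Align the alcohol ANCOVA in protocol 11.5.1.2 with the country effect that SAP 6.2.2 refers to.
3. Name the same term in the longitudinal models of self-reported cocaine use (protocol 11.4.4).
4. Confirm whether centre or country enters the redacted primary model and the urine model in SAP 6.2.3. If it does, only the protocol wording needs to follow.

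The significance condition in SAP 6.2.2 needs no change on this ground.

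The cost is wording and a few degrees of freedom (three for a fixed effect of four countries), with no new data. If centres do not differ, the loss of precision is very slight. It would be larger with many small centres as fixed effects, which is the reason for preferring a random centre effect or country.
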